- 22. Creatinine >2.5 × institutional ULN; total bilirubin >2.5 × ULN; and AST or ALT >3.0 × ULN.
- 23. Breastfeeding or pregnant.
- 24. Concurrent participation in another therapeutic clinical trial.
- 25. Presence of a gastrointestinal ulcer diagnosed by endoscopy within 3 months before screening.

Part 2

- Prior malignancy (other than indolent B-cell NHL), except for adequately treated basal cell or squamous cell skin cancer, in situ cancer, or other cancer from which the subject has been disease free for ≥2 years.
- 2. Known medically apparent CNS lymphoma or

leptomeningeal disease.

- 3. Known evidence of transformation to another aggressive lymphoma.
- 4. A life-threatening illness, medical condition, or organ system dysfunction which, in the investigator's opinion, could compromise the subject's safety, interfere with the absorption or metabolism of acalabrutinib, or put the study outcomes at undue risk.
- 5. Known history of a bleeding diathesis (e.g., hemophilia, von Willebrand disease).
- 6. Significant cardiovascular disease such as uncontrolled or symptomatic arrhythmias, congestive heart failure, or myocardial infarction within 6 months of screening, or any Class 3 or 4 cardiac disease as defined by the New York Heart Association Functional Classification, or QTc using Fridericia formula (QTcF) >480 msec.
- Malabsorption syndrome, disease significantly affecting gastrointestinal function (excluding gastric MALT), or resection of the stomach or small bowel, gastric bypass, symptomatic inflammatory bowel disease, or partial or complete bowel obstruction.
- 8. This criterion was removed under Amendment 5.
- 9. This criterion was removed under Amendment 5.
- 10. Prior exposure to a BCR inhibitor (e.g., BTK or SYK inhibitors).
- 11. For Cohort 2, evidence of CD20- MZL and/or known history of anaphylaxis or hypersensitivity to rituximab (Rituxan/MabThera) or any of its components.
- 12. Ongoing immunosuppressive therapy, including systemic or enteric corticosteroids for treatment or other conditions within 1 week before the first dose of study drug. Note: Subjects may use topical or inhaled corticosteroids or low-dose steroids (≤20 mg of prednisone or equivalent for up to 2 weeks) as therapy for comorbid conditions. However, subjects requiring systemic steroids at daily doses >20 mg prednisone equivalent of systemic exposure are not allowed.
- 13. Grade ≥2 toxicity (other than alopecia or laboratory value requirements mentioned in Part 2) continuing from prior anticancer therapy including radiation.
- 14. Uncontrolled active systemic fungal, bacterial, viral, or other infection (defined as exhibiting ongoing signs/symptoms related to the infection and without improvement, despite appropriate antibiotics or other treatment), or intravenous anti-infective treatment within 2 weeks before first dose of study drug.
- 15. Known history of infection with HIV.
- 16. Serologic status reflecting active hepatitis B or C infection.

- Subjects who are anti-HBc positive and who are surface antigen negative will need to have a negative hepatitis B virus (HBV) DNA polymerase chain reaction (PCR) result before enrollment. Subjects who are HBsAg positive or hepatitis B PCR positive will be excluded.
- Subjects who are anti-HCV positive will need to have a negative PCR result before enrollment. Subjects who are hepatitis C PCR positive will be excluded.
- 17. History of allogeneic stem cell (or organ) transplantation.
- 18. This criterion was removed under Amendment 5.
- 19. Major surgery within 4 weeks before first dose of acalabrutinib.
- 20. Uncontrolled autoimmune hemolytic anemia or idiopathic thrombocytopenia purpura.
- 21. History of stroke or intracranial hemorrhage within 6 months before the first dose of acalabrutinib.
- 22. Requires or receiving anticoagulation with warfarin or equivalent vitamin K antagonist (e.g., phenprocoumon) within 7 days of first dose of study drug.
- 23. Requires treatment with proton-pump inhibitors (e.g., omeprazole, esomeprazole, lansoprazole, dexlansoprazole, rabeprazole, or pantoprazole). Note: this criterion no longer applies to patients who have switched from acalabrutinib capsules to tablets.
- 24. Received a live virus vaccination within 28 days of first dose of study drug.
- 25. ANC <1.0 \times 10⁹/L or platelet count <100 \times 10⁹/L. For subjects with documented disease involvement in the bone marrow, ANC <0.50 \times 10⁹/L or platelet count <30 \times 10⁹/L.
- 26. Creatinine >1.5 × institutional ULN; total bilirubin >1.5 × ULN; and AST or ALT >2.5 × ULN.
- 27. Breastfeeding or pregnant.
- 28. Concurrent participation in another therapeutic clinical trial.
- 29. In the absence of gastric MALT (subject to inclusion criterion 2b) presence of a gastrointestinal ulcer diagnosed by endoscopy within 3 months before screening or diagnosed >3 months before screening and without confirmed resolution by endoscopy.
- 30. Received any chemotherapy, external beam radiation therapy, anticancer antibodies, or investigational drug within 30 days before first dose of study drug.
- 31. History of or ongoing progressive multifocal leukoencephalopathy (PML).

Part 3

- Prior malignancy, except for adequately treated basal cell or squamous cell skin cancer, in situ cancer, or other cancer from which the subject has been disease free for ≥2 years.
- 2. Subjects for whom the goal of therapy is tumor debulking before stem cell transplant.
- 3. Known history or presence of CNS lymphoma or leptomeningeal disease.
- 4. Transformed DLBCL or DLBCL with coexistent histologies (e.g., FL or mucosa-associated lymphoid tissue and primary mediastinal large B-cell lymphoma (PMBCL).
- A life-threatening illness, medical condition, or organ system dysfunction which, in the investigator's opinion, could compromise the subject's safety, interfere with the absorption or metabolism of acalabrutinib, or put the study outcomes at undue risk.
- 6. Known history of a bleeding diathesis (e.g., hemophilia, von Willebrand disease).
- 7. Significant cardiovascular disease such as uncontrolled or symptomatic arrhythmias, congestive heart failure, or myocardial infarction within 6 months of screening, or any Class 3 or 4 cardiac disease as defined by the New York Heart Association Functional Classification, or QTcF >480 msec. Exception: Subjects with controlled, asymptomatic atrial fibrillation during screening are allowed to be enrolled on study.
- 8. Malabsorption syndrome, disease significantly affecting gastrointestinal function, or resection of the stomach or small bowel, gastric bypass, symptomatic inflammatory bowel disease, or partial or complete bowel obstruction.
- 9. Received any chemotherapy, external beam radiation therapy, anticancer antibodies, or investigational drug within 30 days before first dose of study drug.
- 10. Prior exposure to a BCR inhibitor (e.g., BTK or SYK inhibitors), lenalidomide, or CAR-T cell therapy.
- 11. Known history of anaphylaxis or hypersensitivity to rituximab (Rituxan/MabThera) or any of its components.
- 12. Subjects with a prior history of Grade 4 rash associated with thalidomide treatment.
- 13. Ongoing immunosuppressive therapy, including systemic (e.g., IV or oral) corticosteroids within 2 weeks before the first dose of study drug. Note: Subjects may use topical or inhaled corticosteroids or low-dose steroids (≤20 mg prednisone equivalent/day for ≤2 weeks) as a therapy for comorbid

- conditions. During study participation, subjects may also receive systemic (e.g., IV or oral) corticosteroids as needed for treatment-emergent comorbid conditions.
- 14. Grade ≥2 toxicity (other than alopecia or laboratory value requirements mentioned in Part 3 exclusion criteria) continuing from prior anticancer therapy including radiation.
- 15. Uncontrolled active systemic fungal, bacterial, viral, or other infection (defined as exhibiting ongoing signs or symptoms related to the infection and without improvement, despite appropriate antibiotics or other treatment), or intravenous anti-infective treatment within 2 weeks before first dose of study drug.
- 16. Known history of infection with HIV.
- 17. Serologic status reflecting active hepatitis B or C infection.
 - a. Subjects who are anti-HBc positive and who are surface antigen negative will need to have a negative PCR result before enrollment. Subjects who are HBsAg positive or hepatitis B PCR positive will be excluded.
 - b. Subjects who are HCV antibody (anti-HCV) positive will need to have a negative PCR result before enrollment. Subjects who are HCV PCR positive will be excluded.
- 18. History of allogeneic stem cell (or organ) transplantation.
- 19. Major surgery within 4 weeks before first dose of acalabrutinib.
- 20. Uncontrolled autoimmune hemolytic anemia or idiopathic thrombocytopenia purpura.
- 21. History of stroke or intracranial hemorrhage within 6 months before the first dose of acalabrutinib.
- 22. Requires or has received anticoagulation with warfarin or equivalent vitamin K antagonist (e.g., phenprocoumon) within 7 days of first dose of study drug.
- 23. Received a live virus vaccination within 28 days of first dose of study drug.
- 24. ANC <1.0 × 10⁹/L or platelet count <75 × 10⁹/L. Subjects will only be considered eligible if peripheral blood counts can be maintained independent of growth factors or transfusions during screening.
- 25. Creatinine clearance of <60 mL/min, calculated using the formula of Cockcroft and Gault [(140-Age) * Mass (kg)/(72 * creatinine mg/dL) * 0.85 if female].
- 26. Total bilirubin >1.5 × ULN, or AST or ALT >2.5 × ULN, unless directly attributable to Gilbert's syndrome.
- 27. Total bilirubin >1.5 × ULN, or AST or ALT >2.5 × ULN,

unless directly attributable to Gilbert's syndrome. 28. Requires treatment with proton-pump inhibitors (e.g., omeprazole, esomeprazole, lansoprazole, dexlansoprazole, rabeprazole or pantoprazole). Subject receiving proton-pump inhibitors who switch to H2-receptor antagonists or antacids are eligible for enrollment to this study. Note: this criterion no longer applies to patients who have switched from acalabrutinib capsules to tablets. 29. Breastfeeding or pregnant. 30. Concurrent participation in another therapeutic clinical trial. 31. History of or ongoing PML. Dosage Form and As of Clinical Study Protocol (CSP) Version 8.0, acalabrutinib is Strength: supplied in 2 formulations (hard gelatin capsules and orange film coated tablets) for oral administration, prepared using standard pharmaceutical grade excipients. Acalabrutinib capsules and tablets are bioequivalent in relation to dosage strength. Acalabrutinib will be provided in white, high-density polyethylene bottles. Rituximab (Rituxan/MabThera) injection is a commercial product (Genentech, Inc., South San Francisco, CA/Roche, Basal Switzerland). Rituximab is available in 100 mg/10 mL single-use vials and 500 mg/50 mL single-use vials. Lenalidomide (Revlimid) is a commercial product (Celgene, Inc., Summit, NJ). Lenalidomide is available as capsules containing 2.5 mg, 5 mg, 10 mg, 15 mg, 20 mg, and 25 mg of drug substance. Refer to product information from the manufacturers for details on formulation, packaging, and storage of rituximab and lenalidomide.

Dose Regimen/Route of Administration:

Acalabrutinib is intended to be administered orally with 8 ounces (approximately 240 mL) of water. Acalabrutinib taken with an acidic beverage may impact exposure to acalabrutinib (refer to the current Acalabrutinib Investigator Brochure). Acalabrutinib may be administered without regard to food. The capsules or tablets should be swallowed intact and subjects should not attempt to open capsules or crush tablets, and both formulations should not be dissolved in water. Acalabrutinib should be taken BID, approximately 12 hours apart.

Rituximab is to be administered as an IV infusion, not an IV push or bolus. Detailed instructions for the preparation and administration of rituximab are provided in the Rituxan/MabThera package insert and per institutional standards. No dose reductions for rituximab are allowed.

On days when both acalabrutinib and rituximab are administered, the rituximab infusion should begin approximately 1 hour after the acalabrutinib dose.

Part 3

Lenalidomide is to be administered orally at approximately the same time each day, either with or without food. The capsules

	should be swallowed whole with water. The capsules should not be opened, broken, or chewed. Lenalidomide is administered for the first 21 days of each 28-day cycle. On days that both acalabrutinib and lenalidomide are administered, lenalidomide should be taken approximately 30 minutes prior to the first daily dose of acalabrutinib. Dose modification provisions are provided in the protocol.
Concomitant Medications:	The concomitant use of strong inhibitors/inducers of CYP3A (see protocol) should be avoided when possible.
	Acalabrutinib is a substrate of CYP3A4. Drugs inhibiting CYP3A may increase exposure of acalabrutinib. If a subject requires short-term treatment with a strong CYP3A inhibitor (such as anti-infectives for up to 7 days), interrupt acalabrutinib treatment. If a subject requires a moderate CYP3A inhibitor while on study, monitor the subject closely for potential toxicities.
	Conversely, concomitant administration of a strong inducer of CYP3A has the potential to decrease exposure of acalabrutinib and could reduce efficacy. Avoid coadministration of strong CYP3A inducers. If a subject requires treatment with a strong CYP3A inducer, increase the acalabrutinib dose to 200 mg BID during concomitant administration with the strong inducer and return to recommended dose of 100 mg BID after stopping the strong CYP3A inducer.
	Use of proton-pump inhibitors, H2 receptor antagonists, or antacids while taking acalabrutinib capsules has the potential to decrease acalabrutinib exposure. If treatment with a gastric acid-reducing agent is required, consider using a H2-receptor antagonist (2 hours after acalabrutinib capsules) or antacid (2 hours before or 2 hours after acalabrutinib capsules). Avoid coadministration of proton-pump inhibitors with acalabrutinib capsules. Acalabrutinib maleate tablets can be taken without regards to acid-reducing agents (such as antacids, H2-receptor antagonists, or proton-pump inhibitors).
	Lenalidomide
	Subjects who are concurrently receiving digoxin should have periodic monitoring of digoxin plasma levels is due to increased C_{max} and AUC_{inf} of digoxin with concomitant lenalidomide therapy. Moreover, subjects taking concomitant therapies such as erythropoietin-stimulating agents or estrogen-containing therapies, along with lenalidomide, may have an increased risk of venous thromboembolic events per package insert.
	Rituximab
	The only drug-drug interaction with rituximab listed in the Rituxan/MabThera package insert is renal toxicity when used in combination with cisplatin.
Statistics:	Descriptive statistics (including means, standard deviations, and medians for continuous variables and proportions for discrete variables) will be used to summarize data as appropriate. All analyses will be done by indication, treatment, and overall.

Part 1

This study will assess acalabrutinib safety, PK, PD, and antitumor activity when administered alone or in combination with rituximab. The primary objective of this study is to determine the safety as such:

- With a total sample size of 36, the probability of observing one or more instances of an AE with a background rate of 5% and 10% is 84% and 98%, respectively.
- For each treatment arm (n=12 each), the probability of observing one or more instances of an AE with a background rate of 5% and 10% is 46% and 72%, respectively.

Part 2

The primary objective is to characterize the activity of acalabrutinib alone in subjects with R/R MZL as measured by the ORR. Up to 40 subjects in treatment Cohort 1 will provide data for an initial assessment of safety and efficacy of acalabrutinib treatment. Sample size is not based on statistical power consideration.

Part 3

This sample size will provide adequate data for an initial assessment of safety and efficacy of acalabrutinib treatment in combination with lenalidomide and rituximab. This sample size is not based on statistical power consideration.

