3.2 END OF STUDY

The final data cut-off to support final database lock will be based on the projected median follow-up of approximately 30 months for subjects in Part 2 which is projected to occur approximately 23 months after last subject first dose, this is estimated to be approximately 25 August 2023. A median follow-up of approximately 30 months is deemed adequate follow-up for the FL and MZL population in this study. In addition to the above, a final data cut to support Part 1 final database lock will occur approximately 71 months after last subject first dose in Part 1; this is expected to provide adequate long-term follow up for the FL subjects enrolled in the study.

A Clinical Study Report (CSR) will be written using the final data cut-off for Part 1 and a second CSR will be written using the final data cut-off for Parts 2 and 3.

The end of the study is defined as the final data cut-off for the final analysis.

AstraZeneca will continue to supply acalabrutinib in the continued access phase of this study and after completion of this study while, in the opinion of the investigator, the subject is benefitting.

In the event that product development reaches a point where alternative product supply options become available, then these alternative product supply options will be discussed by the Sponsor with the investigator. The Sponsor will work with the investigator to transition the subject(s) to alternative supply, where possible.

It is recommended that investigators continue to observe ongoing subjects at the frequency employed prior to the primary DCO.

Protocol dose modification and stopping criteria are to be followed while a subject is receiving acalabrutinib. A change in the dose/schedule of acalabrutinib should only occur for safety reasons, based on the investigator's judgement, and should generally follow the approach for dose reduction and discontinuation as described in this protocol.

After the final DCO, the clinical database will close to new data, however SAEs must continue to be reported. Subjects may be withdrawn from the study at this time; however, they may remain on study treatment beyond closure of the database if, in the opinion of the Investigator, the subject continues to receive benefit from study treatment. Any subject who is eligible to continue receive acalabrutinib after database closure is considered to have completed the study when he/she meets one of the discontinuation

criteria listed in Section 3.8.

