- 26. Total bilirubin >1.5 × ULN, or AST or ALT >2.5 × ULN, unless directly attributable to Gilbert's syndrome.
- 27. Requires treatment with a strong CYP3a inhibitor/inducer.
- 28. Requires treatment with proton-pump inhibitors (e.g., omeprazole, esomeprazole, lansoprazole, dexlansoprazole, rabeprazole or pantoprazole). Subject receiving proton-pump inhibitors who switch to H2-receptor antagonists or antacids are eligible for enrollment to this study. Note: this criterion no longer applies to subjects who have switched from acalabrutinib capsules to tablets.
- 29. Breastfeeding or pregnant.
- 30. Concurrent participation in another therapeutic clinical trial.
- 31. History of or ongoing PML.

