3.5.7 Dose Modification and Discontinuation

All acalabrutinib dose modifications (Table 1 and Table 2) should be discussed with the medical monitor prior to instituting changes. For toxicities that are common to both acalabrutinib and lenalidomide, consider adjusting the dose of lenalidomide before adjusting the dose of acalabrutinib per the recommendations below:

- Grade 4 neutrophil count decreases (ANC <500/µL) for >7 days (hematopoietic colony-stimulating factors are permitted per American Society of Clinical Oncology [ASCO] guidelines] and use must be recorded on the electronic case report form [eCRF])
- Grade 3 platelet count decreases in the presence of significant bleeding
- Grade 4 platelet count decreases
- Grade 3 or 4 nausea, vomiting, or diarrhea, if persistent despite optimal antiemetic and/or antidiarrheal therapy
- Any other Grade 4 toxicity or unmanageable Grade 3 toxicity

Table 1 Drug Modification and Discontinuation Actions for Acalabrutinib (in Combination with Lenalidomide)

Occurrence	Action
1st–2nd	Hold acalabrutinib until recovery to Grade ≤2 or baseline; may restart at
100 2110	original dose level (100 mg BID)
3rd	Hold acalabrutinib until recovery to Grade ≤2 or baseline; restart at 100 mg
ord	once daily
4th	Discontinue acalabrutinib

BID=twice daily.

Table 2 Drug Modification and Discontinuation Actions for Acalabrutinib (Without

Lenalidomide)

Action
Hold acalabrutinib until recovery to Grade ≤1 or baseline; may restart at
original dose level (100 mg BID)
Hold acalabrutinib until recovery to Grade ≤1 or baseline; restart at 100 mg
once daily
Discontinue acalabrutinib

BID=twice daily.

Whenever possible, any dose adjustment of acalabrutinib should be discussed between the investigator and the Sponsor's medical monitor before implementation. The appropriate clinic staff should dispense the study drug for the new dose level and instruct the subject/caregiver about the change in dose level. Any changes to the dosing regimen must be recorded on the appropriate eCRF.

Rituximab dose modifications should follow the recommendations in the Rituxan/MabThera package insert and institutional standard practices.

Per the lenalidomide label, the dose adjustments listed in Table 3 are acceptable for lenalidomide.

Table 3 Dose Modification Actions for Lenalidomide

Toxicity	Dose Adjustment
Platelets <50 × 10 ⁹ /L:	Interrupt and follow CBC weekly

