3.6.3 Cautionary Therapy Considerations Including Drug-Drug Interactions

Acalabrutinib

The concomitant use of strong inhibitors/inducers of CYP3A (see Appendix 3) should be avoided when possible. Acalabrutinib is a substrate of CYP3A4. Drugs inhibiting CYP3A may increase exposure of acalabrutinib. If a subject requires short-term treatment with a strong CYP3A inhibitor (such as anti-infectives for up to 7 days), interrupt acalabrutinib treatment. If a subject requires a moderate CYP3A inhibitor while on study, monitor the subject closely for potential toxicities.

Conversely, concomitant administration of a strong inducer of CYP3A has the potential to decrease exposure of acalabrutinib and could reduce efficacy. Avoid coadministration of strong CYP3A inducers. If a subject requires treatment with a strong CYP3A inducer, increase the acalabrutinib dose to 200 mg BID during concomitant

administration with the strong inducer and return to recommended dose of 100 mg BID after stopping the strong CYP3A inducer.

Use of proton-pump inhibitors, H2 receptor antagonists, or antacids while taking acalabrutinib capsules has the potential to decrease acalabrutinib exposure. If treatment with a gastric acid-reducing agent is required, consider using a H2-receptor antagonist (2 hours after acalabrutinib capsules) or antacid (2 hours before or 2 hours after acalabrutinib capsules). Avoid coadministration with proton-pump inhibitors with acalabrutinib capsules. Acalabrutinib maleate tablets can be taken without regards to acid-reducing agents (such as antacids, H2-receptor antagonists, or proton-pump inhibitors).

Lenalidomide

Subjects who are concurrently receiving digoxin should have periodic monitoring of digoxin plasma levels due to increased C_{max} and AUC_{inf} of digoxin with concomitant lenalidomide therapy. Moreover, subjects taking concomitant therapies such as erythropoietin-stimulating agents or estrogen-containing therapies, along with lenalidomide, may have an increased risk of venous thromboembolic events per package insert.

Rituximab

The only drug-drug interaction with rituximab listed in the Rituxan/MabThera package insert is renal toxicity when used in combination with cisplatin.

For additional information on potential drug-drug interactions, refer to the individual drug's package insert and Section 3.7.5.

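### After a strong CYP3A inducer the protocol names one return dose, 100 mg BID, which read literally undoes a toxicity reduction to 100 mg once daily

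*Protocol*

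**What the plan says.** The Synopsis (Concomitant Medications) first says to avoid strong CYP3A inducers. If one is required, the site is to "increase the acalabrutinib dose to 200 mg BID during concomitant administration with the strong inducer and return to recommended dose of 100 mg BID" after it stops. Section 3.6.3 repeats the rule with the same fixed end point: "administration with the strong inducer and return to recommended dose of 100 mg BID". Neither place refers to Section 3.5.7 or separates subjects by the dose they were taking before the inducer.

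Section 3.5.7 creates a second, lower dose. With lenalidomide (Table 1), the action at the third occurrence of a listed toxicity is "Hold acalabrutinib until recovery to Grade ≤2 or baseline; restart at 100 mg" once daily. Without lenalidomide (Table 2), the corresponding step is "Hold acalabrutinib until recovery to Grade ≤1 or baseline; restart at 100 mg" once daily. In both tables the next action is to discontinue, and neither has a step back up to 100 mg BID. SAP Section 7.5.3 likewise treats 100 mg per day as the reduced level.

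Three other texts bear on dose changes:

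- Section 3.5.7 opens with: "All acalabrutinib dose modifications (Table 1 and Table 2) should be discussed with the medical monitor prior to instituting changes".
- After Table 2 it adds: "Whenever possible, any dose adjustment of acalabrutinib should be discussed between the investigator" and the sponsor's medical monitor before it is made.
- Section 3.2 says: "A change in the dose/schedule of acalabrutinib should only occur for safety reasons".

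**The concern.** The dose tables and the inducer rule serve different purposes, and they meet in one kind of subject: someone reduced to 100 mg once daily who later needs a strong inducer and then stops it. Under the tables, that subject reached the lower dose through repeated toxicity and has discontinuation as the next step. The inducer rule gives the same subject a return dose equal to the full starting dose. A site that follows the sentence as printed would reverse a tolerability decision through a drug-interaction instruction, without anyone having to judge that the full dose can now be tolerated. What is at stake is the safety of an individual subject, not a trial result.

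**Working it through.** There is no sample size, power or error-rate figure to reproduce. The check sets the two rules side by side and converts them to daily doses.

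**Inputs**

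- Full dose: 100 mg BID (Section 3.1).
- Reduced dose: 100 mg once daily (Section 3.5.7, Tables 1 and 2).
- Dose during a strong inducer: 200 mg BID (Synopsis; Section 3.6.3).
- Stated dose after the inducer: 100 mg BID (same places).
- Cycle length: 28 days (Section 3.1). Unit strength: 100 mg per capsule or tablet (Section 3.5.2).

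**Formula:** daily dose = mg per intake × intakes per day.

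| Stage | Full-dose subject | Reduced subject, literal rule |
|---|---|---|
| Before inducer | 100 × 2 = 200 mg/day | 100 × 1 = 100 mg/day |
| During inducer | 200 × 2 = 400 mg/day (2 times) | 200 × 2 = 400 mg/day (4 times) |
| After inducer | 100 × 2 = 200 mg/day (1 times) | 100 × 2 = 200 mg/day (2 times) |

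Ratios are to the subject's own dose before the inducer. The full-dose subject ends where they began. The reduced subject ends at 200 / 100 = 2 times the earlier dose.

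**Per 28-day cycle after the inducer, reduced subject**

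- Literal rule: 28 × 200 = 5,600 mg, or 56 units of 100 mg.
- Reduced dose kept: 28 × 100 = 2,800 mg, or 28 units.
- Difference: 2,800 mg, or 28 units, per cycle.

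**With a return to the dose before the inducer:** the full-dose subject goes 200 to 200 mg/day (difference 0), and the reduced subject goes 100 to 100 mg/day (difference 0).

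**Do the other texts change the stated return dose?**

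- The opening sentence of Section 3.5.7 is tied to Tables 1 and 2, and the inducer adjustment is in neither table.
- The later sentence covers any acalabrutinib adjustment, but it asks only for a discussion, and only where possible.
- Section 3.2 restricts the reasons for a dose change. It gives no return dose after an inducer.

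**Can the case arise?** Needing a strong inducer is an entry exclusion only in Part 3 (Section 3.4.6, item 27: "Requires treatment with a strong CYP3a inhibitor/inducer"). The Part 1 and Part 2 exclusion lists have no such item, and an entry criterion does not rule out a later need. Treatment may continue until progression or unacceptable toxicity, and Section 3.2 allows it beyond database closure.

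**The case against.** The strongest reply is that the instruction to return presupposes a subject who came from 100 mg BID, so the sentence was never meant for a reduced subject. That is probably what the authors intended. It means the text is not an explicit order to re-escalate, but the sentence still names a dose and exempts nobody.

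A second reply is that Section 3.2 says more than the sentence quoted above. It also requires the protocol's dose-modification and stopping criteria to be followed while a subject takes acalabrutinib, and says that changes should generally follow the protocol's approach to reduction and discontinuation. This points a site back to tables that contain no re-escalation, and it speaks directly to subjects in continued access. Together with the request to involve the medical monitor, which would apply both when the inducer starts and when it stops, it could well catch the case. That stands as mitigation. It leaves a site with two instructions that disagree.

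Third, not every subject below full dose need be one step from stopping. Appendix 8, for example, lets the investigator resume acalabrutinib at a modified dose after COVID-19. This is right, and the safety argument applies most directly to subjects reduced under Tables 1 and 2.

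Fourth, the larger nominal step is the one during the inducer (4 times), and the proposed wording leaves it alone. That dose depends on how far induction lowers exposure and is a clinical choice for the medical monitor. The return dose is a separate matter and can be corrected separately.

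Finally, the practical weight is small. Several uncommon events must coincide, and Section 3.2 projected the final data cut-off for about 25 August 2023. This is why the point is rated minor.

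**Conclusion.** The concern holds as a minor wording fault. For a subject reduced to 100 mg once daily, the printed return dose is twice the dose that the toxicity tables had set.

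This rests on reading the inducer sentence literally and on a subject who has been reduced, is still taking acalabrutinib, and starts and then stops a strong inducer. The documents give no frequency for that sequence and no count of subjects still on drug, and none is assumed here. The general advice to avoid strong inducers makes it rarer still. No endpoint or analysis is affected.

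**What to change.** In the Synopsis (Concomitant Medications) and in Section 3.6.3, replace the fixed return dose with a return to the dose in use before the inducer, once the strong CYP3A inducer has been stopped. Lenalidomide dosing in Table 3 already works this way: it resumes relative to the previous dose.

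The dose during the inducer for a reduced subject stays a matter for the medical monitor; no change to it is proposed.

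The cost is one phrase changed in two places at the next amendment, with no new data, no new procedure and no SAP change. It can help only subjects still receiving acalabrutinib.
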